**7.5.2. Clinical Laboratory Evaluation**

Laboratory tests to be performed, and timing of collection, are detailed in Section 7.2.2 of the protocol and include the following:

- Hematology: Hgb, white blood cell count (WBC), absolute neutrophil count (ANC), lymphocyte count and platelet count.

---

Document: C:\Users\q764206\AppData\Local\Microsoft\Windows\Temporary Internet Files\Content.Outlook\GWW33WM3\ATLAS\_SAPFinal v8.0\_06MAR2018.docx  
 Author: [name] (Updated [name]; [name]; [name], [name])      Version Number:      Final 8.0

Version Date: 06MAR2018

Template No: CS\_TP\_BS016 – Revision 2      Reference: CS\_WI\_BS005  
 Effective Date: 01Feb2010

Statistical Analysis Plan

---

- Chemistry: Total bilirubin, aspartate aminotransferase (AST), alanine aminotransferase (ALT), alkaline phosphatase, albumin, total protein, lactate dehydrogenase (LDH), sodium, potassium, chloride, calcium, phosphate, blood urea nitrogen (BUN)/Urea, creatinine, glucose.
- Urine dipstick for protein (subjects with  $\geq 2+$  protein will have urine protein creatinine [UPC] ratios).
- Pregnancy test, if applicable. Urine pregnancy test will be conducted at sites for females of childbearing potential only. If positive, then serum test should be conducted at central laboratories.
- Thyroid Function: TSH, free T3 and free T4

Baseline laboratory values will be selected from the date closest to but on or prior to the first dose (if there is more than one baseline evaluation).

Summary statistics for actual values and change from baseline will be presented for all planned time points for Hematology, Chemistry, Urinalysis and Thyroid function tests.

Shift from baseline to all post-baseline time points will be produced for urine protein.

Shift from baseline to all post-baseline time points in toxicity grading will be produced for all laboratory parameters which are graded per NCI CTCAE, along with shift from baseline to worst toxicity grade (where worst toxicity grade is defined as the worst toxicity grade experienced at any post-baseline time point, including unscheduled assessments). For laboratory parameters that are graded in both directions e.g. “hyper” and “hypo”, separate rows will be presented for each directional assessment. The hematologic and chemistry laboratory results will be graded according to the NCI CTCAE v4.03 severity grade. For parameters for which an NCI CTCAE v 4.03 scale does not exist, the frequency of subjects with values below, within and above the normal range for the local lab will be summarized.

A summary table of the proportion of subjects meeting Hy’s Law criteria will be provided. The following algorithm will be utilized to determine if Hy’s Law Criteria have been met:

- 1) if ALT|AST baseline is missing, low or normal: Alkaline Phosphatase < 2\*Upper limit of normal (ULN) AND Bilirubin  $\geq 2*ULN$  AND ALT|AST  $\geq 3*ULN$ ;
- 2) if ALT|AST baseline is high: Alkaline Phosphatase < 2\*ULN AND Bilirubin  $\geq 3*ULN$  or (Bilirubin  $\geq 2*ULN$  and Bilirubin  $\geq ULN+Baseline$ ) AND ALT|AST  $\geq 8*ULN$  or (ALT|AST  $\geq 3*ULN$  and ALT|AST  $\geq 2*Baseline$ )

A Hy’s Law Listing will be provided.

---

|           |   |                 |           |
|-----------|---|-----------------|-----------|
| Document: | C:\Users\q764206\AppData\Local\Microsoft\Windows\Temporary Internet Files\Content.Outlook\GWW33WM3\ATLAS_SAPFinal v8.0_06MAR2018.docx |                 |           |
| Author:   | [name] (Updated [name]; [name]; [name], [name])  | Version Number: | Final 8.0 |
|           |   | Version Date:   | 06MAR2018 |

Template No: CS\_TP\_BS016 – Revision 2  
 Effective Date: 01Feb2010

Reference: CS\_WI\_BS005

**Statistical Analysis Plan**

---

All laboratory results will be listed. Any unscheduled laboratory assessments will be listed only.

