#### 7.2.2. Laboratory Safety Assessments

Hematology and blood chemistry will be drawn at the time points described in the Schedule of Activities and analyzed at central laboratories (Refer to Appendix 1). Investigators may have additional blood tests performed for the purpose of planning treatment administration, dose modification, or following adverse events and should be repeated as clinically needed. PT/INR should be performed to monitor patients receiving concomitant warfarin or other anti-coagulants and when clinically indicated.

Thyroid Function Tests (TSH, free T3 and free T4) should be performed for all patients at baseline (Cycle 1Day 1 pre-dose). Subsequently TSH should be done at Cycle 1 Day 15, Cycle 2 Day 1, Cycle 3 Day 1, Cycle 4 Day 1, Cycle 5 Day 1, then every 8 weeks thereafter starting from Cycle 7 Day 1. TSH, free T3, free T4 should be performed on the next visit for any patient who has an elevated TSH in the previous visit. Hypothyroidism should be treated per standard medical practice to maintain euthyroid state with a normal TSH.

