**7.5.4. Vital Signs, Physical Findings, and Other Observations Related to Safety**

Baseline for body weight and vital signs will be defined as the latest value recorded on or prior to dosing on Day 1. Summary statistics for actual values and change from baseline will be presented. Unscheduled body weight and vital signs measurements will be listed only.

The proportion of subjects meeting the following blood pressure criteria on 2 or more scheduled and unscheduled visits (need not be consecutive) after first dose (modified from JNC criteria to address single measurement per time point) (Chobanian et al., 2003) will be presented in a table:

- Normal: Systolic Blood Pressure (SBP)  $<120$  mmHg and Diastolic Blood Pressure (DBP)  $< 80$  mmHg
- Pre-hypertension\*: SBP 120-139 mmHg or DBP 80-89 mmHg
- Stage 1: SBP 140-159 mmHg or DBP 90-99 mmHg
- Stage 2: (SBP  $\geq 160$  mmHg and DBP  $<120$ ) or DBP 100-119 mmHg

\*Defined according to CTCAE v4.03 criteria.

The proportion of subjects with weight loss  $\geq 10\%$  after first dose will also be presented in a table.

ECOG PS and change from baseline in ECOG PS will be summarized using summary statistics, and will also be presented as a shift from baseline to post-baseline time points. Specifically, shift tables of ECOG score from baseline will be presented at each cycle as well as tables demonstrating from baseline to best and worst post baseline score. A mixed model will also be implemented to assess treatment differences in ECOG PS over time. Baseline ECOG will be

---

|           |   |                 |           |
|-----------|---|-----------------|-----------|
| Document: | C:\Users\q764206\AppData\Local\Microsoft\Windows\Temporary Internet Files\Content.Outlook\GWW33WM3\ATLAS_SAPFinal v8.0_06MAR2018.docx |                 |           |
| Author:   | [name] (Updated [name]; [name]; [name], [name])  | Version Number: | Final 8.0 |
|           |   | Version Date:   | 06MAR2018 |

Template No: CS\_TP\_BS016 – Revision 2  
 Effective Date: 01Feb2010

Reference: CS\_WI\_BS005

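### The SAP's listed-only rules for unscheduled results contradict its own safety tables, and read literally they could undercount the Hy's Law, weight-loss and normal-range tables

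*SAP*

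**What the plan says.** SAP 7.5.2 (Clinical Laboratory Evaluation) plans a shift from baseline to worst toxicity grade and defines the term inclusively: "where worst toxicity grade is defined as the worst toxicity grade experienced at any post-baseline time point, including unscheduled assessments". It also plans a Hy's Law table ("A summary table of the proportion of subjects meeting Hy’s Law criteria will be provided") and, for parameters without a CTCAE scale, the frequency of subjects below, within and above the local normal range. Neither of these says whether unscheduled results count. The section then ends: "Any unscheduled laboratory assessments will be listed only".

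SAP 7.5.4 (Vital Signs) follows the same pattern. It states "Unscheduled body weight and vital signs measurements will be listed only", yet its next paragraph builds the blood-pressure category table from subjects meeting a criterion "on 2 or more scheduled and unscheduled visits (need not be consecutive) after first dose". A further table gives "The proportion of subjects with weight loss" of 10% or more after first dose, with nothing on unscheduled weights.

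The protocol foresees off-schedule testing. Section 7.2.2 says "Investigators may have additional blood tests performed for the purpose of planning treatment administration, dose modification, or following adverse events", and Section 6.2 allows unscheduled assessments around safety events and early discontinuation of treatment. Scheduled assessments under Section 6.2.2 take place every 4 weeks up to Cycle 5 Day 1, then every 8 weeks.

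**The concern.** Each section gives two rules for the same kind of data, and neither limits its general rule to particular outputs. Two programmers working from this SAP could produce different safety tables.

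The more consequential problem is in the tables that carry no inclusion wording. For the Hy's Law proportion, the weight-loss table and the normal-range frequencies, the listed-only rule is the only stated rule. The authors did write unscheduled values into some tables, so silence elsewhere can fairly be read as exclusion. On that reading, a subject who meets the combined ALT/AST, bilirubin and alkaline phosphatase criteria only on an unscheduled panel is left out of the Hy's Law proportion.

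Unscheduled tests are not a random sample of time. The protocol links them to safety events, dose modification and adverse-event follow-up. If they are excluded, more data are lost from the arm with more toxicity, and an undercount would tend to shrink the difference between arms in those tables. Safety is a secondary objective of this placebo-controlled adjuvant trial, so the proportions by arm should be right.

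**Working it through.** No published figure has to be reproduced. The check sets the rules side by side and then illustrates how often a scheduled draw could miss a short abnormality.

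**Step 1. Which rule reaches each output**

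| Output | SAP section | Specific wording on unscheduled values | General rule | Result |
|---|---|---|---|---|
| By-visit laboratory statistics | 7.5.2 | Planned time points only | Listed only | Consistent |
| Worst-grade shift | 7.5.2 | Included | Listed only | Contradiction; specific wording probably prevails |
| Hy's Law proportion | 7.5.2 | None | Listed only | Excluded if read literally |
| Normal-range frequencies | 7.5.2 | None | Listed only | Excluded if read literally |
| Blood-pressure categories | 7.5.4 | Included | Listed only | Contradiction; specific wording probably prevails |
| Weight loss of 10% or more | 7.5.4 | None | Listed only | Excluded if read literally |

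SAP 6.2.2 does not settle the matter. It fixes the denominators of the laboratory tables and does not say which results count towards a worst or any-time value.

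**Step 2. Scheduled coverage**

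Inputs from Protocol 6.2.2: the interval between scheduled draws is L = 28 days up to Cycle 5 Day 1, and L = 56 days after that. Assumption, not in the documents: an abnormality lasts d = 14 to 28 days, with onset uniform over the interval. Visit windows are ignored.

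Chance that a scheduled draw falls inside the abnormality = min(1, d / L).

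- 4-weekly phase: 14/28 = 50%; 28/28 = 100%.
- 8-weekly phase: 14/56 = 25%; 28/56 = 50%.

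Cycle 1 Day 1 to Cycle 5 Day 1 is 4 × 4 = 16 weeks. A patient treated for the full 3 years (3 × 52 = 156 weeks) spends about 16/156 = 10% of that time in the 4-weekly phase. The documents do not say how toxicity is spread over time, so the two phases cannot be weighted into one figure.

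**Step 3. What this does and does not show**

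The complement (0–50% in the first phase, 50–75% in the second) is the share that scheduled draws would miss. It is not the share lost from the tables. Some of these abnormalities would never be tested at all, and graded ones found on unscheduled tests would still enter the worst-grade shift under its own definition. The calculation is for laboratory draws. A sustained weight loss would be seen at the next scheduled weighing, so the weight table is probably the least sensitive of the three.

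**The case against.** The best case for the SAP is that the listed-only sentences were meant for by-visit summaries. In 7.5.4 the sentence directly follows the one on summary statistics, and the next paragraph brings unscheduled visits back in. In 7.5.2 the summary statistics are tied to planned time points. A specific rule normally overrides a general one, so the worst-grade and blood-pressure tables would be built correctly. The Hy's Law algorithm and the weight-loss table carry no visit restriction of their own, so a sensible programmer might include everything.

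Other planned outputs also help. All laboratory results are listed and a Hy's Law listing is planned. Protocol 8.4 makes test results that change dosing or need intervention reportable as adverse events. SAP 7.5.1.2 tabulates hepatic disorders and hypertension as events of special interest.

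Much of this stands. A reader might infer that worst grades and high blood pressures found between visits will drop out of the tables. The documents do not support that, because both tables have explicit inclusion wording. A reader might also infer that the worst values are generally found off schedule. The protocol only permits extra tests, and repeat tests during recovery may record falling values after a scheduled peak.

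The objection does not remove the gap in the other three outputs. The likely intent is nowhere written, and the only rule stated points the other way. Listings give no proportion by arm, and adverse-event terms do not reproduce the Hy's Law algorithm.

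**Conclusion.** The concern holds, within limits. Both contradictions are in the current SAP text. For the worst-grade shift and the blood-pressure table, the practical risk is low. For the Hy's Law proportion, the table of weight loss of 10% or more and the normal-range frequencies, a literal reading excludes unscheduled values and could undercount cases, more so in the arm with more toxicity.

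The size of the effect is unknown. The documents give no count of unscheduled results or Hy's Law cases, and the percentages above rest on an assumed duration and random onset.

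Two stronger conclusions go too far. One is that losing one or two Hy's Law cases would change the hepatic conclusion; nothing in the documents supports that. The other is that axitinib would look safer across the safety output as a whole. Adverse-event tables and listings would still carry much of the information, and SAP 7.5 plans no formal safety comparison between arms. The primary and secondary efficacy analyses are unaffected. The point should be fixed, but it does not threaten the trial's main result.

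**What to change.** Replace the listed-only sentences in SAP 7.5.2 and 7.5.4 with one common rule:

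> Unscheduled assessments are excluded from by-visit summary statistics and by-visit shift tables only. Unscheduled post-baseline values are included in all worst-value and any-time analyses: worst CTCAE grade shift, normal-range frequencies for ungraded parameters, Hy's Law, blood-pressure categories and weight loss of 10% or more.

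Two small additions would prevent further questions. State that the Hy's Law listing also covers unscheduled results. Say whether the normal-range frequencies are any-time counts per subject or counts by visit; if a by-visit version is also produced, leaving unscheduled values out of that version is appropriate.

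The cost is a change of SAP wording and of the matching table specifications. The results are already collected and listed, so no new data and no protocol change are needed.

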**7.5.3. ECG Evaluations**

ECG evaluations are performed at screening only in this study.

The number and percentage of subjects with Normal, Abnormal not Clinically Significant, Abnormal Clinically Significant and Unevaluable reading at screening will be summarized by treatment group.

Summary statistics for QT Interval, Heart Rate, RR Interval, QT corrected for heart rate using Bazett’s method (QTcB) and QT corrected for heart rate using Fridericia’s method (QTcF) will be produced by treatment group using categories as defined in the International Conference on Harmonisation (ICH) E14 guideline (i.e., QTcF millimeter/second [ms]:  $\leq 450$ ;  $>450 - \leq 480$ ;  $>480 - \leq 500$ ;  $>500$ ).

All ECG results will be listed.

**7.5.4. Vital Signs, Physical Findings, and Other Observations Related to Safety**

Baseline for body weight and vital signs will be defined as the latest value recorded on or prior to dosing on Day 1. Summary statistics for actual values and change from baseline will be presented. Unscheduled body weight and vital signs measurements will be listed only.

The proportion of subjects meeting the following blood pressure criteria on 2 or more scheduled and unscheduled visits (need not be consecutive) after first dose (modified from JNC criteria to address single measurement per time point) (Chobanian et al., 2003) will be presented in a table:

- Normal: Systolic Blood Pressure (SBP)  $<120$  mmHg and Diastolic Blood Pressure (DBP)  $< 80$  mmHg
- Pre-hypertension\*: SBP 120-139 mmHg or DBP 80-89 mmHg
- Stage 1: SBP 140-159 mmHg or DBP 90-99 mmHg
- Stage 2: (SBP  $\geq 160$  mmHg and DBP  $<120$ ) or DBP 100-119 mmHg

\*Defined according to CTCAE v4.03 criteria.

The proportion of subjects with weight loss  $\geq 10\%$  after first dose will also be presented in a table.

ECOG PS and change from baseline in ECOG PS will be summarized using summary statistics, and will also be presented as a shift from baseline to post-baseline time points. Specifically, shift tables of ECOG score from baseline will be presented at each cycle as well as tables demonstrating from baseline to best and worst post baseline score. A mixed model will also be implemented to assess treatment differences in ECOG PS over time. Baseline ECOG will be

---

|           |   |                 |           |
|-----------|---|-----------------|-----------|
| Document: | C:\Users\q764206\AppData\Local\Microsoft\Windows\Temporary Internet Files\Content.Outlook\GWW33WM3\ATLAS_SAPFinal v8.0_06MAR2018.docx |                 |           |
| Author:   | [name] (Updated [name]; [name]; [name], [name])  | Version Number: | Final 8.0 |
|           |   | Version Date:   | 06MAR2018 |

Template No: CS\_TP\_BS016 – Revision 2  
 Effective Date: 01Feb2010

Reference: CS\_WI\_BS005

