## **6.2.2.** Treatment Procedures Subsequent Cycles

Assessments other than tumor imaging should be done at Day 1 of every cycle (4 weeks) until Cycle 5 Day 1, then every 8 weeks thereafter starting from Cycle 7 Day 1.

- a. Physical examination of major body systems.
- b. Body weight and vital signs (temperature, 2 BP readings separated by at least 5 minutes, pulse rate).
- c. ECOG PS.
- d. Laboratory tests.
  - Hematology: Hgb, WBC, ANC, lymphocyte count and platelet count.
  - Chemistry: Total bilirubin, AST, ALT, alkaline phosphatase, albumin, total protein, LDH, sodium, potassium, chloride, calcium, phosphate, BUN/Urea, creatinine, glucose.
  - Urine Dipstick for protein (patients with  $\geq 2+$  protein will have UPC).
  - Thyroid function tests: TSH. Hypothyroidism should be treated per standard medical practice to maintain euthyroid state with a normal TSH (TSH, Free T3

and free T4 should be performed on the next visit for any patient who has an elevated TSH.).

- e. Tumor imaging including CT or MRI of the chest, abdomen, and pelvis should be performed every 16 weeks for the first 3 years from the initiation of study treatment. Additional imaging and/or local histo-/cytopathology confirmation, if clinically indicated, of potential disease sites should be performed whenever recurrence or occurrence of a secondary malignancy is suspected. Brain CT or MRI with contrast or bone scan (confirmatory imaging in addition to bone scan may be required), if clinically indicated.
- f. Assessment of concomitant medications and treatments.
- g. Assessment of study drug compliance/accountability.
- h. Assessment of adverse events and tumor-related signs and symptoms.

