## 7.2.3. Other Safety Assessments

**Physical examination**: A physical examination including, but not limited to, general appearance, head, skin, neck, eyes, ears, nose, mouth, throat, breast, lungs, heart, abdomen, back, lymph nodes, extremities, thyroid, musculoskeletal, pulses and nervous system will be performed. The physical examination will include examination of known and suspected sites of disease.

**Height and body weight**: Height will be recorded at screening visit only. Body weight will also be recorded at the start of each 4 week period.

**Vital Signs**: Measurements will be made of temperature, BP and pulse rate. 2 BP readings should be taken at least 5 minutes apart in the seated position after the patient has been sitting quietly for 5 minutes.

All patients will be issued a blood pressure monitor and blood pressure measurement diary. Patients will be asked to record their blood pressure measurements prior to taking each dose of study drug (twice daily) for the first 3 months, and once a week thereafter. Following dose modification of study drug or anti-hypertensive medication, or changes of anti-hypertensive medication, patients should restart blood pressure measurements prior to taking each dose of study drug for the first 3 months and once a week thereafter. Patients should record all blood pressure measurements in their patient diary. BP readings should be taken in the seated position after the patient has been sitting quietly for 5 minutes. Patients should be instructed to inform the investigator immediately if their sBP rises above 150 mm Hg, dBP rises above 100 mm Hg, or if they develop symptoms perceived to be related to elevated BP (eg, headache, visual disturbance).

**ECOG PS**: The ECOG PS scale will be used (Appendix 2). Evaluation of ECOG PS at screening should reflect the patient condition just prior to nephrectomy.

All safety assessments should be repeated as clinically needed.

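### The measured blood-pressure table in SAP 7.5.4 has overlapping and incomplete rows, and its two-visit rule assumes one reading per visit where the protocol takes two

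*SAP*

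**What the plan says.** SAP 7.5.4 presents the proportion of subjects meeting the "blood pressure criteria on 2 or more scheduled and unscheduled visits (need not be consecutive) after first dose". It explains the rule as "modified from JNC criteria to address single measurement per time point". The row limits are:

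- Normal: systolic below 120 and diastolic below 80.
- Pre-hypertension: "SBP 120-139 mmHg or DBP 80-89 mmHg".
- "Stage 1: SBP 140-159 mmHg or DBP 90-99 mmHg".
- Stage 2: systolic 160 or more with diastolic below 120, "or DBP 100-119 mmHg".

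No rule ranks the rows or assigns a subject to the worst one. The same section says that unscheduled vital signs appear in listings only.

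Protocol 7.2.3 states as a general rule that "2 BP readings should be taken at least 5 minutes apart in the seated position". Protocol 6.2.2 repeats it for Cycle 2 onward: "Body weight and vital signs (temperature, 2 BP readings separated by at least 5 minutes, pulse rate". Protocol 6.2.1.2 (Day 15, when done as a visit) and 6.2.3 (end of treatment) ask for the same. Protocol 5.3.4.2 and its Table 4 act on two high readings taken at a single visit.

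**The concern.** The table has four weaknesses.

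- **Premise.** The two-visit rule stands in for a second reading that the protocol already requires at the same visit.
- **Rows.** The limits are joined by "or" with no hierarchy, so one reading can fall in two rows. Diastolic values of 120 or more are not properly covered.
- **Counting.** A single confirmed high visit does not count. Nor do two high visits that fall in different rows. The section counts unscheduled visits in the table while sending unscheduled measurements to listings only.
- **Exposure.** There is no time limit or exposure adjustment, so subjects with more visits have more chances to qualify.

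This matters because hypertension is a leading expected toxicity: 40% all grades and 16% Grade 3/4 on axitinib in protocol Table 1. This is also the SAP's only categorical summary of measured blood pressure; the rest of 7.5.4 gives values and changes from baseline.

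**Working it through.** The documents give no figure for this table, so there is none to reproduce.

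**Step 1: test readings against the rows as written.**

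| Reading | Rows met |
|---|---|
| 125/95 | Pre-hypertension and Stage 1 |
| 165/85 | Pre-hypertension and Stage 2 |
| 145/105 | Stage 1 and Stage 2 |
| 150/125 | Stage 1 only |
| 170/125 | none |

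The last two arise because both arms of the Stage 2 definition stop below a diastolic of 120. The highest diastolic values are therefore dropped or placed in a lower row.

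**Step 2: apply the two-visit rule to whole subjects.**

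- One visit at 165/85, controlled afterwards: Stage 2 is met once, so the subject is in neither hypertension row.
- One visit at 150/85 and one at 165/85: Stage 1 once and Stage 2 once, so again neither hypertension row. The diastolic of 85 meets Pre-hypertension twice, so that is where this subject is counted.

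**Step 3: count post-dose visits** (Schedule of Assessments and protocol 6.2.2). Cycle 1 Day 15 falls at week 2, and Day 1 of Cycles 2 to 5 at weeks 4, 8, 12 and 16. Visits then run every 8 weeks from Cycle 7 Day 1 (week 24).

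- By week 52: 1 + 4 + 4 = 9.
- By week 156: 1 + 4 + 17 = 22.

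If Day 15 is done by telephone the counts are 8 and 21. End-of-treatment and unscheduled visits would add to them.

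**Step 4: chance of qualifying with unchanged risk.** Let q be an assumed constant chance per visit of meeting a row, and n the number of visits. With independent visits,

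P(at least 2) = 1 − (1−q)^n − n·q·(1−q)^(n−1).

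For q = 0.03:

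- n = 9: 1 − 0.7602 − 0.2116 = 0.028.
- n = 22: 1 − 0.5117 − 0.3481 = 0.140.

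| Assumed q | 1 year (9 visits) | 3 years (22 visits) |
|---|---|---|
| 2% | 1.3% | 7.1% |
| 3% | 2.8% | 14.0% |
| 5% | 7.1% | 30.2% |

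**Step 5: relax independence.** Readings within a person are correlated. A beta-binomial model with mean 3% and assumed correlation ρ, with a = 0.03(1/ρ − 1) and b = 0.97(1/ρ − 1), gives:

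| Assumed ρ | 1 year | 3 years | Ratio |
|---|---|---|---|
| 0 | 2.8% | 14.0% | 5.0 |
| 0.1 | 6.0% | 15.3% | 2.6 |
| 0.2 | 6.5% | 13.0% | 2.0 |
| 0.3 | 6.3% | 10.9% | 1.7 |
| 0.5 | 5.4% | 7.9% | 1.4 |

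The proportion rises with time on treatment in every case. The size depends heavily on the assumed correlation.

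**Step 6: check whether a one-visit rule would remove this.** With independent visits at 3%, P(at least 1) = 1 − 0.97^n, which is 24.0% at 9 visits and 48.8% at 22. A worst-visit table repairs the counting but not the dependence on exposure.

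**The case against.** The strongest reply is that hypertension does not depend on this table. Protocol 8.4 makes an abnormal finding an adverse event when it needs medical intervention, changes dosing or leads to significant added treatment, so an episode treated after one visit should reach the adverse-event data. SAP 7.5.1.2 lists hypertension as an event of special interest, with Kaplan-Meier time to first occurrence if there are at least 10 events per arm. SAP 7.5.1 provides risk differences and risk ratios with confidence intervals, and 7.5 plans no formal safety comparison between arms. All of this stands. A reader might infer that the plan loses promptly treated hypertension altogether; the documents do not support that.

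A reader might also infer a five-fold distortion, or a reversed arm comparison. The five-fold ratio needs independent visits. A reversal can be constructed: under independence, 4% per visit over 9 visits gives 4.8%, below the 7.1% from 2% per visit over 22. But the documents show no such difference in exposure between arms, so bias in the comparison is conditional. Constant risk is also a simplification, because treatment after a first high visit should lower later risk.

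The undercounting mechanism is narrower than the whole table. Protocol 5.3.4.2 acts above 150 systolic or 100 diastolic, so many Stage 1 values trigger no action.

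The case report form is not in the documents, and the SAP phrase may describe what is recorded rather than what is taken. Footnote 6 of the Schedule of Assessments mentions no second reading. That makes this a conflict to reconcile rather than proof of a mistake. If only one value is stored, the SAP should say which.

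Finally, a subject appearing in several rows across different visits is not in itself an error, since the table does not claim exclusive categories. One reading meeting two rows, and a very high reading meeting none, are faults all the same.

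**Conclusion.** The concern holds for this table. The overlap, the gap at diastolic 120 and above, the two kinds of omitted subject and the unclear handling of unscheduled visits follow from the SAP wording and need no assumption. The single-measurement premise conflicts with protocol 6.2.1.2, 6.2.2, 6.2.3 and 7.2.3.

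The dependence on time on treatment is certain in direction but not in size. At an assumed 3% per visit, the three-year proportion is 1.4 to 2.6 times the one-year proportion for assumed correlations from 0.5 down to 0.1, and 5.0 times under independence. It distorts the arm comparison only if time on treatment differs between arms, and the table has no safeguard if it does.

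The table is descriptive, does not touch the primary analysis, and sits beside a separate adverse-event analysis of hypertension. The correction is still worth making because the table cannot be read reliably as written.

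**What to change.** Revise SAP 7.5.4 as follows:

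1. Assign each visit to the single highest category met, using both readings if both are recorded; otherwise state which reading is used.
2. Define the top category so that diastolic values of 120 or more are included.
3. State that unscheduled visits count in this table, and reconcile that with the listings-only sentence.
4. Tabulate each subject once, by worst post-dose visit category.
5. Add the same table for a common early window, such as the first 16 weeks, or a Kaplan-Meier estimate of time to first Stage 2 visit. Item 4 alone does not remove the dependence on exposure.

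These are reporting categories only and leave the protocol's management limits untouched.

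The cost is SAP wording, one reprogrammed table and one added summary. No new data are needed if both readings were recorded. The downside is that a transient high value at one visit now counts; the two-visit version can be kept as a supplementary row.
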